5. STUDY ASSESSMENTS AND PROCEDURES

5.1. Study Flow Chart

A detailed study flow chart (with all assessments) is displayed below.

Study procedures	Screening Visit	Baseline Visit	Control Visits	Day 28 / D56	End of Study treatment visit	FU visit	FuS visit Cohort 1&3	FuS visit Cohort 2
	Screening 21 ± 7 days	Baseline	Cohort 2 only ± 2 days	Cohort 3 only ± 2 days	28-Day (Cohort 1&2), 84-Day (Cohort 3) ± 2 days	FU visit 1-week post completion ± 2 days	FU visit 4 weeks post completion ± 7 days	FU visit 4 weeks post completion ± 7 days
Informed Consent	X	Day 1	Day 7, 14, 21	Day 28 / D56	Day 28 / Day 84	Day 35 / Day 91	Day 56 / Day 112	Day 56
Inclusion/Exclusion Criteria	X							
ECG	X	X			X		X	X
Adverse Event reporting	X	X	X	X	X	X	X	X
Concomitant medication checks and	X	X	X	X	X	X	X	X
Physical examination and vital signs	X	X	X	X	X	X	X	X
Hematology & Biochemistry	X	X						
Syphilis, HBV/HCV serology	X							
HIV-1 antibody serology #	X							
Urine and Rectal GC/CT (NAAT)	X				X	X	X	X
TNR & PT	X	Δ			Δ	Δ	Δ	Δ
HIV-1 viral load \$	X	X			X*	X	X	X
CD4+ and CD8+ counts \$	X	X			X*	X	X	X
Pharmacokinetics: Plasma and PBMC		0h, 0.5h, 1h, 1.5h, 2h, 4h, 6h and 8h	X*	X*	0h, 0.5h, 1h, 1.5h, 2h, 4h, 6h and 8h	X Trough	X Trough	X Trough
Flexible sigmoidoscopy for Rectal Biopsy		X			X*	X	X	X
- Explant infection #	X				X*	X	X	X
- MMC flow cytometry	X				X*	X	X	X
- Rectal microbiome	X				X*	X	X	X
- Rectal proteomics	X				X*	X	X	X
- Rectal transcriptomics	X				X*	X	X	X
- Rectal tissue pharmacokinetics	X				X*	X	X	X
- Rectal HIV Reservoir \$	X				X*	X	X	X
Blood samples for Immunology & Molecular assays		X			X*	X	X	X
- PBMC flow cytometry	X				X*	X	X	X
- Plasma SCAs \$	X				X*	X	X	X
- Plasma inflammatory markers	X				X*	X	X	X
Blood samples for HIV reservoir assays \$		X			X	X	X	X
- PBMC HIV reservoir \$	X				X	X	X	X

CT; Chlamydia trachomatis, GC; Neisseria gonorrhoea, HBV; hepatitis B virus, HCV; hepatitis C virus, INR; international normalized ratio, NAAT; nucleic acid amplification testing, MMC; mucosal mononuclear

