5.2. Study Endpoints

- Primary endpoint:
Main pharmacokinetic parameters (Cmax, AUC) after first dose of ABX464 (Day 1):
 - Cohort 1: at Day 28 and at Day 56 for plasma, PBMC and rectal tissue.
 - Cohort 2: at Day 28 and at Day 56 for plasma and PBMC. Rectal tissue only at Day 28.
 - Cohort 3: at Day 28, Day 84 and Day 112 for plasma, PBMC and rectal tissue.
 -
- Secondary endpoints:
 - Number and grade of treatment-emergent adverse events, including treatment-emergent serious adverse events, adverse events leading to investigational product discontinuation, during the study;
 - Change in GALT HIV reservoirs in rectal tissue from Baseline to Day 28 and Day 56 in HIV-infected subjects (Cohort 1) and from Baseline to Day 28, Day 84 and Day 112 (Cohort 3);
 - Change in total viral DNA in the reservoir cells from Baseline to Day 28 and Day 56 in HIV-infected subjects (Cohort 1) and from Baseline to Day 28, Day 84 and Day 112 (Cohort 3);
 - Change in inflammatory markers in plasma from Baseline to Day 28 and Day 56 in subjects enrolled in Cohort 1 & 2 and to Day 28, Day 84 and Day 112 in subjects enrolled in Cohort 3;
 - Change in immunophenotype and assessment of cell-activation markers from Baseline in PBMCs and MMC, using an 11-colours panel, including: CD3, CD8, CD4, CD45RA, CCR7, CD27, CD28, CD38, HLA-DR, PD-1, viability to Day 28 and Day 56 in subjects enrolled in Cohort 1 & 2 and to Day 28, Day 84 and Day 112 in subjects enrolled in Cohort 3;
 - Change in HIV-1 RNA, CD4+ and CD8+ counts from Baseline to Day 28 and Day 56 in HIV-infected subjects (Cohort 1) and from Baseline to Day 28, Day 84 and Day 112 (Cohort 3);
 - Change of rectal microbiota using taxonomic markers from Baseline to Day 28 and Day 56 in subjects enrolled in Cohort 1, **change of rectal microbiota using taxonomic markers from Baseline to Day 28 in subjects enrolled in Cohort 2 and to Day 28, Day 84 and Day 112 in subjects enrolled in Cohort 3;**
 - Change in the transcriptome & proteome from Baseline to Day 28 and Day 56 in subjects enrolled in Cohort 1, **change in the transcriptome & proteome from Baseline to Day 28 in Cohort 2 and to Day 28, Day 84 and Day 112 in subjects enrolled in Cohort 3.**

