- Viral Load, CD4/CD8 count (HIV infected Subjects);
- Perform PK blood sample (at 9AM \pm 1hour);
- Adverse event assessment.

5.3.8. End of Study Visit (D56 for cohort 1&2 or D112 for cohort 3; \pm 7 days)

- Physical examination and vital signs;
- Microbiome specimen collection (swabs);
- Hematology (incl. INR and PT if clinically indicated);
- Biochemistry;
- Urine GC/CT NAAT & Rectal GC/CT NAAT;
- HIV serology (HIV uninfected participants)
- 12 lead ECG;
- Viral Load, CD4/CD8 count (HIV infected Subjects);
- Blood collection for HIV reservoir assessment (HIV infected Subjects) and immuno-evaluation;
- Flexible sigmoidoscopy with collection of rectal biopsies (Cohort 1 and 3 only)
- Perform PK blood sample (at 9AM \pm 1hour);
- Adverse event assessment.

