7.3. Study Discontinuation

All subjects, regardless of the completion or premature discontinuation, should perform the End of Study Visit (EoS) according to the study flow-chart. In case a premature discontinuation this EoS visit should occur within the next two weeks after the last dosing and should include but depending on the subject willingness the PK evaluation and the sigmoidoscopy.

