8.4. Time Period, and Frequency of Detecting AEs and SAEs

All AEs and SAEs occurring from the time a subject consents to participate in the study until 4 weeks after he or she has completed or discontinued the investigational product must be recorded in the subject's eCRF. Importantly, SAEs will have to be reported to ABIVAX or its designee within 24 hours of awareness of an SAE.

Legislative guidance requires also reporting any **related** SAEs to be reported after the subject finished the study if the investigator becomes aware of them.

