#### 4.3 Pharmacokinetic Endpoint

ABX464 has a very short  $t_{1/2}$  (1 to 2 h) and generally no drug could be quantified after 10h post-dose, so steady-state is virtually reached at the second administration.

NGlcABX464 (main ABX464 metabolite) has a  $t_{1/2}$  of 90 to 110 h, meaning that steady-state is reached after 19 to 22 days of administration.

Pharmacokinetic parameters are assessed in plasma, in PBMC and in rectal mucosa.

Intensive Pharmacokinetic runs are conducted after the first dose of ABX464 (Day 1) and for

② Cohort 1: at Day 28 and at Day 56 for plasma, PBMC and rectal tissue.

② Cohort 2: at Day 28 and at Day 56 for plasma and PBMC. Rectal tissue only at Day 28.

② Cohort 3: at Day 28, Day 84 and Day 112 for plasma, PBMC and rectal tissue.

Following PK parameters will be derived for ABX464 and ABX464-N-glucuronide

- $C_{max}$ ,  $t_{max}$ : the maximum plasma concentration ( $C_{max}$ ) and the time taken to reach  $C_{max}$  ( $t_{max}$ ) will be obtained directly from the concentration-time data.
- $AUC_{0-\tau}$ : the area under the concentration-time curve from time zero to the time of dosing interval  $\tau$  (24 h post-dose for ABX464 and ABX464-N-glucuronide). If no concentration can be measured at this time point,  $AUC_{0-last}$  (from time zero to the last quantifiable concentration)

will be calculated. Both parameters will be presented independently. For both parameters, a linear trapezoidal method will be used.

In addition, five rectal biopsies at each time point will be sent to ALTANBIO for tissue PK determination.

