## 9 Data

## 10 Statistical Methods

### 10.1 General Principles

All statistical methods will be based on the International Conference on Harmonisation (ICH) E9 document "Statistical Principles for Clinical Trials".

Data will be summarised by cohort. A total column showing all patients will be included for baseline and safety summaries. Where appropriate, data will also be summarised by visit with summaries for each visit attended as scheduled and an additional summary for final (last scheduled visit or early withdrawal). The format of the summaries is defined in the shells in a separate document.

All summary tables will be made up of the following three columns:

- Cohort 1: Hiv infected subjects receiving the 150mg dose of ABX464 for 28 days;
- Cohort 2: Hiv uninfected subjects receiving the 50mg dose of ABX464 for 28 days;
- Cohort 3: Hiv infected subjects receiving the 50mg dose of ABX464 for 84 days.

In addition, summary tables for total DNA will be made up with an additional column of cohort 1 and Cohort 3 pooled.

In summary and analysis tables of continuous variables, standard descriptive statistics (N, mean, standard deviation [SD], median, quartiles, minimum, maximum ) will be presented when relevant. 95% confidence Intervals (CI) will be presented in the statistical analysis outputs as appropriate. For PK summaries, arithmetic mean (AM), geometric mean (GM) and coefficient of variation (%CV) will be used to summarise the data. The minimum and maximum statistics will be presented in summary tables to the same number of significant figures as the original data. The mean/AM, median, GM, CI, SD and will be presented to one more significant than the original data.

For numeric data which includes non-numeric values (e.g. PK data reported as BLQ or lab results reported as < 10 or >100) the following principles will be applied when summarising the data:

- BLQ will be replaced with a value that is ½ of the lower limit of quantification (LLQ)
- Results reported as < x will be treated in the same way as BLQ with LLQ=x
- Otherwise AM, GM, SD, CI and %CV will not be calculated
- Whenever meaningful, minimum, median and maximum will be presented based on the reported data (e.g. minimum = <10, median = 20, maximum = >100)

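### Day 56/112 PK concentrations are summarised by nominal visit, although the ±7-day End of Study window alone allows an 8- to 13-fold spread in the plasma metabolite

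*Protocol*

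**What the plan says.** The primary endpoint includes the End of Study (EoS) time point. For Cohort 1, for example, Protocol 5.2 reads "Cohort 1: at Day 28 and at Day 56 for plasma, PBMC and rectal tissue"; Cohort 3 has Day 112. The sample comes from the "End of Study Visit (D56 for cohort 1&2 or D112 for cohort 3" (Protocol 5.3.8), which the flow chart in Protocol 5.1 anchors as "FU visit 4 weeks post completion ± 7 days". SAP 3.4 repeats the ±7 days and gives every other on-treatment or post-treatment visit ±2 days. One PK sample is drawn at EoS. Its clock time is fixed (9 AM, give or take an hour), but its time since last dose is not.

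SAP 4.3 gives the N-glucuronide a half-life "of 90 to 110 h, meaning that steady-state is reached after 19 to 22 days of administration". The parent's half-life is 1 to 2 h. Protocol 5.4.8 says that the Day 35 and Day 56 samples are there to describe terminal decay.

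On analysis, Protocol 9.2.1 presents concentrations by treatment and time point, SAP 10.1 summarises by visit, and SAP 11.3.1 summarises the primary endpoint descriptively on the FAS, repeated on the PP set if applicable. Out-of-window visits are flagged in listings. Neither document relates the EoS concentration to actual time since last dose.

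For subjects who stop early, Protocol 7.3 states that "this EoS visit should occur within the next two weeks after the last dosing", with PK and sigmoidoscopy depending on willingness. SAP 10.1 adds "an additional summary for final (last scheduled visit or early withdrawal".

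**The concern.** A 14-day window is harmless for a slowly changing measurement. A drug concentration during washout falls by a constant proportion per unit of time, and here the window spans more than three half-lives. Samples that are all within protocol, and therefore neither flagged nor removed from the PP set, can sit at very different points on the decline and still be averaged as one Day 56 or Day 112 value. The spread in that cell then mixes differences in disposition with differences in appointment date, and a summary by nominal visit cannot separate the two. The loss matters most for the purpose that the protocol gives these samples, because a decay cannot be described without the time axis.

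A related gap concerns early leavers. They stay in the FAS, which needs only one dose and baseline data. A sample taken within 14 days of last dose is not comparable with one taken at 28 days, and the plan does not say how such samples are classified for PK.

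**Working it through.** **Inputs.** Half-life h = 90 to 110 h (SAP 4.3, Protocol 5.4.8). EoS at 28 ± 7 days after completion, i.e. 21 to 35 days, a width of 14 × 24 = 336 h (Protocol 5.1). Early-leaver EoS at up to 14 days (Protocol 7.3). Cohort size 12. Assumption: mono-exponential decline in plasma at the stated half-life.

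**The plan's own figure.** Taking steady state as five half-lives (my convention): 5 × 90/24 = 18.75 days and 5 × 110/24 = 22.9 days, against the stated 19 to 22 days. It reproduces, with the upper end apparently truncated.

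**Fraction of the end-of-dosing level left after d days** = 2^(−24d/h):

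| Days after last dose | h = 90 h | h = 110 h |
|---|---|---|
| 14 | 7.5% | 12.0% |
| 21 | 2.1% | 4.2% |
| 28 | 0.57% | 1.45% |
| 35 | 0.16% | 0.50% |

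**Ratio from visit date alone** = 2^(gap in hours/h):

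- Edge to edge, day 21 to day 35 (336 h): 2^(336/110) = 8.3; 2^(336/90) = 13.3.
- Edge to nominal day 28 (168 h): 2^(168/110) = 2.9; 2^(168/90) = 3.65.
- A ±2-day window, edge to edge (96 h): 2^(96/110) = 1.8; 2^(96/90) = 2.1.
- Early leaver at day 14 against nominal day 28 (336 h): again 8.3 to 13.3.

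**A wider reading.** If EoS is counted as study Day 56 ± 7 (Days 49 to 63) and the last dose moves with the ±2-day end-of-treatment visit (Days 26 to 30), the interval runs from 49 − 30 = 19 to 63 − 26 = 37 days. The edge-to-edge ratio over 18 days (432 h) is then 2^(432/110) = 15 to 2^(432/90) = 28. The 21-to-35-day figures are the conservative ones.

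**Effect on a cohort mean.** With 3 of 12 subjects at day 21 and 9 at day 28, the arithmetic mean rises by (9 + 3 × 2.88)/12 = 1.47 to (9 + 3 × 3.65)/12 = 1.66. With 3 at day 35 instead, it falls to 0.82 to 0.84 of its nominal value.

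**Effect on a comparison of two cohorts.** Suppose visits are spread uniformly over the 14 days (an assumption). The SD of log concentration due to timing is (ln 2 × 336/h)/√12 = 0.61 (110 h) to 0.75 (90 h). The standard error of a 12-versus-12 log difference is that SD × √(2/12) = 0.25 to 0.31, a factor of about 1.3 to 1.4.

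**Parent drug.** At day 21 (504 h), at least 504/2 = 252 half-lives have passed. Only the metabolite is at issue.

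**The case against.** The other side has a good deal to say, and most of it limits the consequences rather than the core.

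A reader might infer that a few early or late visits would move a cohort mean several-fold. They would not: three of twelve at the earliest permitted day raise it about 1.5- to 1.7-fold. The 8- to 13-fold figure compares opposite edges of the window, not a departure from schedule.

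A reader might also infer that differences between cohorts would chiefly reflect appointment dates. Nothing in the documents suggests that dates differ systematically by cohort, so the effect is scatter, not bias. Other sources of difference are large: Cohort 1 receives three times the dose of the others, and the stated half-life range alone gives 1.45/0.57, about 2.6-fold, at exactly day 28. No formal comparison is planned at Day 56/112; the only one, in Protocol 9.2.1, is at Day 28.

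The early-leaver part is weaker than it may look. SAP 10.1 puts early withdrawal in the separate final summary, SAP 11.3.1 lists no final summary for PK, such subjects are replaced, and their PK sample depends on willingness. Entry into the Day 56/112 cell is not shown.

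It is also tempting to see a conflict between Protocol 7.3 and Protocol 8.4, which records adverse events "until 4 weeks after he or she has completed or discontinued the investigational product". Section 8.4 sets a recording period, not a visit, so an EoS visit by week 2 does not contradict it.

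Nor do the documents show that residual exposure of 0.16 to 4.2% alters the reservoir or immune readings taken at the same visit.

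What survives is that compliant samples 14 days apart share one cell, the PP repeat removes neither, and the plan leaves out the time axis that its stated purpose needs.

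**Conclusion.** The point stands as an avoidable loss of precision and interpretability, with a cheap remedy. For the plasma N-glucuronide, visit date alone can produce an 8.3- to 13.3-fold difference between two compliant samples, or 2.9- to 3.65-fold against nominal day 28. The result is extra noise in the Day 56/112 summary and a weaker account of terminal decay, not a demonstrated bias between cohorts.

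The figures rest on mono-exponential decline at the stated plasma half-life. No half-life is given for PBMC or rectal tissue, so the size there is unknown. The limit of quantification is not stated either, and some late samples may fall below it. The quantity concerned is a single concentration, since one sample cannot yield Cmax or AUC.

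**What to change.** In SAP 11.3.1 and Protocol 9.2.1, report and plot the Day 35/91 and Day 56/112 concentrations against actual time since last dose, not by nominal visit only. Either fit a log-linear decline for each subject or adjust each EoS value to 28 days after last dose. Last-dose date is already needed for exposure (SAP 11.5), the subject diary records intake times (Protocol 6.3.1), and visit dates are needed to flag out-of-window visits (SAP 10.1). Sample date and time should be carried into the PK dataset.

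State in the SAP that EoS samples taken under Protocol 7.3 after early withdrawal are listed separately, with their time since last dose, and are not pooled with 28-day post-dose values in the Day 56/112 or final PK summaries.

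A narrower EoS PK window for subjects who have not yet reached that visit is optional. It would reduce appointment flexibility and add major deviations, because time-window non-compliance counts as one (Protocol 9.1.1). It could not apply to Cohort 1, whose Day 56 interim analysis SAP 8 reports as done, so cohorts would have different windows. The analysis change alone deals with most of the problem, at the cost of a little more analysis work.

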5.4. Detail of the study assessments

5.4.1. Physical Examination and Vital Signs

A routine physical examination (including body weight) will be done at each study visit. Physical examination at baseline will cover eyes, ears, nose, throat, lungs/thorax, heart/cardiovascular system, abdomen, skin and mucosae, nervous system, lymph nodes, musculoskeletal system, and, if applicable, others. At follow up, physical exams will be symptom directed. Any new clinically relevant finding compared to baseline must be documented as adverse event.

Measurements of vital signs will be done at each visit (Blood pressure, Heart Rate, Body temperature). The subject should rest for at least 15 minutes prior to measurements. The measurements can be performed either in sitting or supine position of the subject. The right or left arm may be used. However, the position and the arm used for measurement should be kept constant throughout the trial for an individual subject.

The investigator should ensure that each parameter outside the normal range is assessed for clinical significance. For any deviation assessed clinically significant, the investigator has to document the change as an AE in the CRF.

In addition, it is at the discretion of the investigator to document any change or trend over time in vital signs as an AE if he considers the change to be clinically significant, even if the absolute value is within the alert limit or reference range.

5.4.2. ECG

Electrocardiograms have to be done at all study visits. A 12-lead ECG with recordings of at least 6 action potentials in lead II (paper speed 25mm/s, amplitude 10mm/mV) has to be done in a resting position. Prior to the recording the subject should be at rest for at least five minutes. Resting ECG should be performed before any examinations.

The ECG printout will be reviewed by the investigator and a signed and dated copy of the ECG will be attached to the medical file. The original ECG printouts are considered as source data and should be stored at site. In case thermal paper is used, a copy of the original ECG must be kept as well. All abnormal findings must be documented in the CRF. Any clinically relevant findings compared to Visit V0 must be documented as adverse events.

5.4.3. Hematology and biochemistry

For hematology and biochemistry local laboratories will be used. All laboratory results and reference ranges for safety parameters must be entered in the eCRF. Each laboratory value that is outside of the institution's normal range will be identified. The investigator will be responsible for assessing the clinical significance of laboratory abnormalities. If the investigator is uncertain about the clinical significance of a laboratory abnormality, he/she will consult with the Sponsor medical monitor. The investigator should follow any clinically significant laboratory abnormalities until resolution.

Table 4 displays the clinical laboratory parameters that must be measured at every visit.

Table 4: Laboratory Tests

HEMATOLOGY		BIOCHEMISTRY
Hemoglobin		Sodium
Hematocrit		Potassium
WBC		Chloride
Neutrophils		Calcium
Lymphocytes		Phosphate
Monocytes		Glucose
Eosinophils		BUN or urea
Basophils		Creatinine
Platelet count		AST
INR		ALT
PT		Alkaline phosphatase
		Total bilirubin
		GLDH
		Total protein
		Lipase
		Albumin
		LDH
		gGT
		CRP

5.4.4. Viral load and HIV Reservoirs assessment

Regarding HIV-1 viral load, local laboratories will be used as this is done in routine for HIV infected subjects and as

method is standardized so that comparisons between laboratories can be performed.

Viral persistence will be assessed by quantification of total HIV DNA and cell-associated RNA in peripheral blood CD4 T cells and in rectal mucosal leukocytes. In addition, ultrasensitive viral load in plasma will be also assessed.

Experimental design:

Longitudinal analysis of proviral HIV DNA: CD4+ T cells will be isolated by positive selection from total PBMC. Pellets from all time points of each patient (pre- and post-treatment with ABX464) will be lysed, and proviral HIV DNA will be measured by digital droplet PCR (ddPCR, BioRad). Two pairs of primers located in different regions of the viral genome will be used, in order to avoid technical amplification problems due to HIV-1 variability and not due to a real small reservoir. The results will be normalized by the number of cells in each reaction, which will be quantified in parallel through primers targeting the cellular gene RPP30.

Longitudinal analysis of CA-HIV RNA: CD4+ T cells will be isolated by positive selection from total PBMC. Pellets from all time points of each patient (pre- and post-treatment with ABX464) will be lysed, and CA-HIV RNA will be measured by droplet digital PCR (ddPCR, BioRad). Two pairs of primers located in different regions of the viral genome will be used. The results will be normalized by the number of cells in each reaction, which will be quantified in parallel through primers targeting a house-keeping gene.

Longitudinal analysis of plasma VL: ultrasensitive analysis of the VL will be carried out by Single-Copy Assay (SCA) in plasma. Briefly, 10ml of plasma from all time points of each patient (pre- and post-treatment with ABX464) will be concentrated by ultracentrifugation and the determination of the VL will be then performed by the Abbott system. This technique allows detecting down to 1 copy/ml of HIV.

